8.2.3 Additional

Effects on biomarkers of mechanism of action and inflammation, and liver function will be evaluated as additional endpoints.

Title: A Multicenter, Double-Blind, Randomized Trial of IDN-6556 in Subjects Who had Hepatitis C Virus (HCV) Reinfection and Liver Fibrosis or Cirrhosis following Orthotopic Liver Transplantation for Chronic HCV Infection and Who Subsequently Achieved a Sustained Virologic Response Following anti-HCV Therapy

8.2.4 Exploratory

An assessment of morphometric image analysis to quantify collagen deposition will be performed on liver histology.

8.3 Specific Study Visit Information

The following sections provide specific details of the assessments to be performed at each study visit. After a subject is entered into the study, the visit window from Day 1 to Month 6 will be \pm seven days. After Month 6, the visit window will be \pm 14 days. However, every effort should be made to maintain the nominal visit schedules of subjects as predicated by the date of the Month 0/Day 1 visit.

Except at Screening, the liver biopsy window will be \pm 42 days. In the event that a subject is withdrawn from the study prior to the 24 month visit, the subject will be contacted and asked to sign a separate consent to return for a Month 24 liver biopsy unless a biopsy was performed within 42 days of the Month 24 visit.

8.3.1 Screening Phase (Week -6 to Day 0)

The following study evaluations will be performed during the course of the Screening period:

- Signed informed consent
- Inclusion and exclusion criteria
- Complete medical and surgical histories
- Record of concomitant medication usage, including use of prescription and over-the-counter medications, and vitamin, mineral, and/or herbal supplements/therapies
- Subject demographics
- Vital signs (blood pressure, pulse, respiratory rate, and temperature)
- Complete physical examination, including height and weight
- Liver and abdominal ultrasound (prior ultrasound, or superior imaging, may be utilized if performed within 3 months of Screening)
- 12-Lead ECG
- Chest X-ray
- Liver biopsy (refer to the biopsy window in **Section 8.1.1**)
- Transient elastography (at select centers only)
- Clinical chemistry, hematology, and coagulation
- Urinalysis
- α -fetoprotein

Title: A Multicenter, Double-Blind, Randomized Trial of IDN-6556 in Subjects Who had Hepatitis C Virus (HCV) Reinfection and Liver Fibrosis or Cirrhosis following Orthotopic Liver Transplantation for Chronic HCV Infection and Who Subsequently Achieved a Sustained Virologic Response Following anti-HCV Therapy

- Serum pregnancy test (for women of childbearing potential)

Since the Screening Phase can last up to 6 weeks, it is highly recommended that only key assessments and laboratory tests initially be conducted to confirm a subject's eligibility after signing of the informed consent document. The remainder of the screening assessments should only be performed for those subjects who pass the initial screening assessments.

Clinically meaningful, unexpected findings in the laboratory or clinical tests that may interfere with the study conduct need to be discussed with the Medical Monitor prior to entry into the study.

Once the subject's eligibility is confirmed, including confirmation of the fibrosis score by the central histopathologist, the subject will be randomized by IWRS to either IDN-6556 or placebo, and stratified by degree of Baseline Ishak Fibrosis Score (F2, F3-F5 or F6).

Subjects who initially fail screening may be re-screened after discussion with the Conatus Medical Monitor. Reasons for initial screen failure and eligibility for re-screening will be clearly documented.

8.3.2 Double-Blind Phase (Month 0/Day 1 through to Month 24/ Early Termination/ End of Treatment)

The following study evaluations will be performed during Double-Blind Phase as noted on the Schedule of Events:

- Record concomitant medications and therapies
- Vital signs (blood pressure, respiratory rate, pulse, and temperature)
- Physical examination, including weight, at yearly intervals
- 12-lead ECG at yearly intervals
- Liver and abdominal ultrasound every 6 months
- Transient elastography every 6 months (at select centers only)
- Liver biopsy at yearly intervals – refer to **Section 8.1.1** for requirements for additional biopsies
- Study drug administration and dispensation
- Compliance assessment (capsule count)
- Record adverse events
- Clinical chemistry and hematology. On Day 14, only clinical chemistry will be performed – refer to **Section 8.1.9** for requirements for additional laboratory and clinical assessments for safety

Title: A Multicenter, Double-Blind, Randomized Trial of IDN-6556 in Subjects Who had Hepatitis C Virus (HCV) Reinfection and Liver Fibrosis or Cirrhosis following Orthotopic Liver Transplantation for Chronic HCV Infection and Who Subsequently Achieved a Sustained Virologic Response Following anti-HCV Therapy

- Coagulation at Month 0/Day 1, Month 1, Month 6, and every 6 months thereafter
- Urinalysis at Month 0/Day 1 and every 6 months thereafter
- Blood sample for immunosuppressant concentration monitoring (Month 0/Day 1 and Day 14)
- Collection of up to 10 mL of blood for immunosuppressant pharmacokinetic analysis at predose, and at 0.5, 1, 2, 3, 4, 5, and 8 hours post dose at Month 1
- α -fetoprotein every 6 months[^]
- CA 19-9 at Month 0/Day 1 and Month 24
- Collection of 12 mL of blood for serum biomarkers at Month 0/Day 1, Day 14, Months 1, 3, 6, 12, and 24 (Note: ELF test to be conducted every 6 months only)
- Collection of 5 mL of blood for population pharmacokinetic analysis at Months 12 and 24
- Collection of 5 mL of blood for pharmacokinetic analysis at predose, and at 0.5, 1, 2, 3, 4, 5, and 8 hours post dose at Month 1
- Collection of 5 mL of blood for pharmacokinetic analysis if repeat laboratory testing is required for elevated ALT, AST, and/or total bilirubin values
- Serum pregnancy test (for women of childbearing potential); except Month 0/Day 1, and Day 14
- Urine pregnancy test (for women of childbearing potential) at Month 0/Day 1 prior to study drug administration

The study procedures specified for Month 0/Day 1 should be performed prior to dosing with study drug.

In the event that a subject is withdrawn from the study prior to the 24 Month visit, the subject will be contacted and asked to sign a separate consent to return for the Month 24 liver biopsy. If premature discontinuation is within approximately 42 days of the originally scheduled Month 24 visit, the liver biopsy may be performed at the time of premature discontinuation.

[^] If elevations occur during the Double-Blind Phase of the study, Investigators should utilize normal clinical practice for follow-up of subjects and discuss treatment (dis)continuation with the Conatus Medical Monitor.

Title: A Multicenter, Double-Blind, Randomized Trial of IDN-6556 in Subjects Who had Hepatitis C Virus (HCV) Reinfection and Liver Fibrosis or Cirrhosis following Orthotopic Liver Transplantation for Chronic HCV Infection and Who Subsequently Achieved a Sustained Virologic Response Following anti-HCV Therapy

8.3.3 Follow-Up Phase (Month 25, 4 Weeks after Early Termination/End of Treatment)

All subjects will be seen four weeks after end of treatment. Follow-up procedures will consist of the following:

- Update of concomitant medications and therapies
- Vital signs (blood pressure, respiratory rate, pulse, and temperature)
- Physical examination, including weight
- Update of adverse events
- Clinical chemistry, hematology, and coagulation
- Urinalysis
- Collection of 12 mL of blood for serum biomarkers
- Serum pregnancy test (for women of childbearing potential)

If the subject discontinues the study early, all reasonable attempts should be made to complete the final follow-up phase, which may or may not coincide with the M24 liver biopsy.

8.4 Prior and Concomitant Medications

All prescription and 'over-the-counter' (OTC) medications, including supplements, taken by the subject during the 30 days before Screening will be recorded on the Concomitant Medications case report form. The generic drug name, indication, total daily dose, and dates of drug administration will be recorded. Any additions, deletions, or changes in the dose of these medications should be entered on the case report form.

Any current ongoing medications, including OTC drugs, will be allowed if not prohibited by the protocol and approved by the Investigator. Subjects must be instructed not to take any new OTC drugs during the study without first obtaining approval from the Investigator. Subjects should also be instructed to contact the Investigator if they develop any illnesses or any new medications.

Subjects should not take the following:

- Potentially hepatotoxic drugs (starting 30 days prior to dosing and throughout the study)
- Any drugs known to cause fibrosis, with the exception of immunosuppressive therapy (for six months prior to dosing and throughout the study)

It is expected that all subjects will be receiving immunosuppressant therapy during the course of the study. This should be tailored to the specific subject's

Title: A Multicenter, Double-Blind, Randomized Trial of IDN-6556 in Subjects Who had Hepatitis C Virus (HCV) Reinfection and Liver Fibrosis or Cirrhosis following Orthotopic Liver Transplantation for Chronic HCV Infection and Who Subsequently Achieved a Sustained Virologic Response Following anti-HCV Therapy

requirements. The reasons for any changes in background immunosuppressant therapy should be documented in the case report forms and the subject should continue with all study related procedures. In the event that a subject develops liver transplant rejection during the study, decisions about a subject's treatment regimen, including whether or not the subject will continue in the study, will be completely at the discretion of the Investigator.

8.5 Other Precautions, Restrictions, Drugs, and Alcohol

All subjects must take appropriate precautions to avoid excessive sun exposure due to the increased risk of malignancies, especially skin malignancies, with their requisite, long-term use of immunosuppressants. Subjects should also be advised that illicit drugs, drugs of abuse and excessive alcohol use will not be allowed from the start of the Screening to the end of the follow-up visits. If there is clear evidence of use of illicit drugs, drugs of abuse, or excessive alcohol use during study drug treatment, the Investigator must counsel the subject and determine whether continued study participation is appropriate.

8.6 Subject and Study Termination

8.6.1 Reasons and Procedures for Early Termination

Subjects may be withdrawn from the study at their own request, upon request of the Investigator, or by the Sponsor at any time and for any reason. Reasons for removing a subject from the study may include:

- the subject does not adhere to study rules and procedures;
- the subject wishes to withdraw from the study ;
- the subject develops an AE necessitating withdrawal, or requires an unacceptable concomitant medication;
- continuation of the subject is in violation of the inclusion and/or exclusion criteria;
- the Investigator feels it is in the subject's best interest to terminate participation;
- the study is terminated by the Sponsor.

All subjects who discontinue the study because of adverse events (AEs) will be followed up at suitable intervals in order to evaluate the course of the AE and to ensure the resolution or stabilization of the abnormality.

Title: A Multicenter, Double-Blind, Randomized Trial of IDN-6556 in Subjects Who had Hepatitis C Virus (HCV) Reinfection and Liver Fibrosis or Cirrhosis following Orthotopic Liver Transplantation for Chronic HCV Infection and Who Subsequently Achieved a Sustained Virologic Response Following anti-HCV Therapy

All subjects who prematurely discontinue the study, regardless of the cause, will be contacted and asked to sign a separate consent to return for a Month 24 liver biopsy. If premature discontinuation is within approximately 42 days of the originally scheduled Month 24 visit, the liver biopsy may be performed at the time of premature discontinuation.

However, subjects should undergo all other assessments during the final visit, scheduled for End of Treatment on the date of discontinuation (see **Sections 8.3.2** and **Appendix I**). A follow-up visit should be scheduled to occur 4 weeks following the early termination visit.

Female subjects who are discontinued prematurely due to a pregnancy should be followed as outlined in **Section 10.0**.

If a subject is lost to follow up (i.e., fails to return for study visits), reasonable efforts should be made to contact the subject and complete study termination procedures, in addition to the long-term follow-up of the subject.

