1.0 STUDY SYNOPSIS

Protocol:

IDN-6556-07

Title:

A Multicenter, Double-Blind, Randomized Trial of IDN-6556 in Subjects Who had Hepatitis C Virus (HCV) Reinfection and Liver Fibrosis or Cirrhosis Following Orthotopic Liver Transplantation for Chronic HCV Infection and Who Subsequently Achieved a Sustained Virologic Response Following anti-HCV Therapy

Phase of Trial:

Phase 2

Objectives:

Primary

- To assess the effect of oral IDN-6556 on fibrosis or cirrhosis using the Ishak Fibrosis Score, in subjects with HCV reinfection and liver fibrosis or cirrhosis following orthotopic liver transplantation for chronic HCV who subsequently achieved a sustained virologic response following anti-HCV therapy

Secondary

- To determine the effects of oral IDN-6556 on necro-inflammatory sub-score of the modified Histological Activity Index
- To determine the effects of oral IDN-6556 on markers of mechanism of action and inflammation
- To assess the safety and tolerability of oral IDN-6556 in subjects status post orthotopic liver transplantation

Centers:

Multicenter, approximately 35 sites in the US.

Number of Subjects:

Approximately 60 subjects (40 subjects on IDN-6556: 20 on placebo) will be assigned in a 2:1 ratio to IDN-6556 25 mg BID or placebo. Up to 15 subjects with an Ishak score of F6 can be enrolled.

Design:

This is a double-blind, randomized, multicenter study involving subjects with chronic HCV who underwent liver transplantation; developed HCV-related liver fibrosis or cirrhosis; achieved a sustained virologic response (SVR) following anti-HCV therapy;

Title: A Multicenter, Double-Blind, Randomized Trial of IDN-6556 in Subjects Who had Hepatitis C Virus (HCV) Reinfection and Liver Fibrosis or Cirrhosis following Orthotopic Liver Transplantation for Chronic HCV Infection and Who Subsequently Achieved a Sustained Virologic Response Following anti-HCV Therapy

[figure not shown]
and still show demonstrable fibrosis or cirrhosis on liver biopsy. Upon successful screening, subjects will be randomized to receive 25 mg BID of IDN-6556 or placebo in a 2:1 ratio.

The randomization will be stratified based on the stage of fibrosis or cirrhosis at Baseline:

1. Ishak F2
2. Ishak F3 – F5
3. Ishak 6

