5. Willingness to utilize two reliable forms of contraception (for both males and females of childbearing potential) from Screening to one month after the last dose of study drug

Key Exclusion Criteria:

1. Known active infection with hepatitis B virus (HBV) and/or human immunodeficiency virus (HIV)
2. History of renal transplant and/or severe renal impairment defined as eGFR (estimated glomerular filtration rate) of less than 30 mL/min/1.73 m²
3. Evidence of tumor burden >Milan criteria, or evidence of micro- or macrovascular invasion in explanted liver
4. Hepatocellular carcinoma (HCC) at entry into the study
5. Concurrent sirolimus (rapamycin) use

Title: A Multicenter, Double-Blind, Randomized Trial of IDN-6556 in Subjects Who had Hepatitis C Virus (HCV) Reinfection and Liver Fibrosis or Cirrhosis following Orthotopic Liver Transplantation for Chronic HCV Infection and Who Subsequently Achieved a Sustained Virologic Response Following anti-HCV Therapy

6. History or presence of clinically concerning cardiac arrhythmias, or prolongation of Screening (pre-treatment) QTcF interval of > 480 milliseconds (msec)
7. Subjects with diagnosed or suspected systemic lupus erythematosus (SLE) and/or rheumatoid arthritis (RA)
8. If female: known pregnancy, positive urine or serum pregnancy test, or lactating/breastfeeding.

Criteria for Evaluation:**Safety Variables:**

Safety evaluations will be based on adverse event (AE) reports. These will be coded using MedDRA to preferred terms, sorted by body system, and compared between the two treatment groups.

1. Serious adverse events will be analyzed separately
2. Clinical laboratory variables will be evaluated in the context of coinciding clinical adverse events when necessary

Efficacy Variables:Efficacy Endpoints:

- Ishak Fibrosis Score
- Necro-inflammatory sub-score of the modified Histological Activity Index
- Biomarkers of apoptosis
- Liver function (e.g., ALT, AST, bilirubin)
- Transient elastography (to be performed at select centers only)

Exploratory Endpoint:

- Morphometric image analysis to quantify collagen deposition

Statistical Methods:

All endpoints will be tested at a two-sided statistical significance level of 0.05.

For the comparison of Ishak Fibrosis Scores at 24 months, subjects will be classified into one of the following three categories:

- Category 1. Regression at 24 months defined as a greater than or equal to a one point improvement in Ishak Fibrosis Score from Baseline.

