7.1 Inclusion Criteria

To participate in this study, subjects must meet **all** of the following criteria:

1. Male or female subjects of minimum adult legal age (according to local laws for signing the informed consent document), able to provide written informed consent, and able to understand and willing to comply with the requirements of the study
2. History of orthotopic liver transplantation for HCV-induced liver disease
Note: Living donor or cadaveric transplantation will be permitted into the study. HCV positive donor livers will also be permitted into the study.
3. Diagnosis of HCV infection (HCV-RNA detectable in serum) and liver fibrosis or cirrhosis status post liver transplantation, and achieved a sustained virologic response (SVR) with anti-viral HCV treatment within 18 months of Day 1
Note: For the purposes of this study, subjects must meet the definition of SVR as defined by the anti-HCV regimen used.
4. Liver fibrosis or cirrhosis on liver histology as read by central histopathologist of Ishak F2 to F6 within three months of Day 1
Note: Baseline liver histology in close approximation of the three month window may be permitted on a case by case basis after discussion with the Medical Monitor.
5. Available liver tissue for central read (ten, 4-microns-thick, unstained liver sections)
6. Willing to undergo protocol-determined liver biopsies during the study
7. Hemoglobin ≥ 11 g/dL, platelet count $\geq 75 \times 10^9/L$, WBC $\geq 2.0 \times 10^9/L$
Note: As these parameters may be influenced by immunosuppressive therapy, small variances may be permitted on a case by case basis after discussion with the Medical Monitor.
8. On stable doses of immunosuppressant therapy for ≥ 3 months prior to Day 1
9. Willingness to utilize two reliable forms of contraception (for both males and females of childbearing potential) from Screening to one month after the last dose of study drug

Title: A Multicenter, Double-Blind, Randomized Trial of IDN-6556 in Subjects Who had Hepatitis C Virus (HCV) Reinfection and Liver Fibrosis or Cirrhosis following Orthotopic Liver Transplantation for Chronic HCV Infection and Who Subsequently Achieved a Sustained Virologic Response Following anti-HCV Therapy

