12.5 Sample Size

The sample size determination for this study is based on the Phase 2b screening methodology presented in Fleming and Richardson¹².

A total of 60 subjects will be treated in a 2:1 ratio to IDN-6556 or placebo. Treatment duration for all subjects will be two years. The primary outcome variable is change in Ishak Fibrosis Score at 24 months.

The primary analysis of this Phase 2 “screening” study is formally based on a three-category decision guideline. To be specific, the decision guideline for this study is based on whether the proportion of subjects who show a regression (i.e., improvement) of Ishak Fibrosis Score at 24 months for the IDN-6556 arm compared to the placebo arm is less than 5%, is from 5% up to 15%, or is at least 15%.

Note that these categories should not be interpreted as providing strict decision rules but rather as guidelines that will be factored into a broader scientific assessment of the benefit to risk profile of the IDN-6556 regimen. This broader assessment will include consideration of safety, of secondary efficacy endpoints, and of relevant information external to this study. Specifically, the decision guidelines for this study are:

1. If the estimated absolute increase in the proportion of subjects who show regression in Ishak Fibrosis Score is less than 5%, (e.g., less than an estimated increase from 30% to 35%), then the IDN-6556 regimen is not plausibly more efficacious than placebo; the formulation of this IDN-6556 regimen or its utility in this indication will be reconsidered.
2. If the estimated absolute increase in the proportion of subjects who show regression in Ishak Fibrosis Score is from 5% up to 15%, (e.g., an estimated increase from 30% to between 35% and 45%), then the IDN-6556 regimen is

Title: A Multicenter, Double-Blind, Randomized Trial of IDN-6556 in Subjects Who had Hepatitis C Virus (HCV) Reinfection and Liver Fibrosis or Cirrhosis following Orthotopic Liver Transplantation for Chronic HCV Infection and Who Subsequently Achieved a Sustained Virologic Response Following anti-HCV Therapy

plausibly more efficacious than placebo and if analyses of biomarkers suggest utility of the IDN-6556 regimen, should be evaluated definitively in a subsequent Phase 3 clinical study.

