12.6.3 Efficacy Analysis

Primary Endpoint: Change from Baseline in Ishak Fibrosis Score at 2-years

The primary analysis of the primary endpoint will test the change in Ishak Fibrosis Scores at 24 months between the treatment groups in the FAS Population using ITT principles.

Subjects will be classified into one of the following 3 categories:

- Category 1. Regression at 24 months defined as a greater than or equal to a one point improvement in Ishak Fibrosis Score from Baseline.

Title: A Multicenter, Double-Blind, Randomized Trial of IDN-6556 in Subjects Who had Hepatitis C Virus (HCV) Reinfection and Liver Fibrosis or Cirrhosis following Orthotopic Liver Transplantation for Chronic HCV Infection and Who Subsequently Achieved a Sustained Virologic Response Following anti-HCV Therapy

- Category 2. Stable disease at 24 months defined as no change from Baseline in the Ishak Fibrosis Score from Baseline.
- Category 3. Progression at 24 months defined as a greater than or equal to a one point worsening from Baseline in the Ishak Fibrosis Score from Baseline or death/re-transplantation.

Changes in the Ishak Fibrosis Score at 24 months will be analyzed by a logistic regression model, appropriate for the analysis of ordinal categorical data, to derive the odds ratio and associated 95% confidence interval for IDN-6556 against placebo. The model will allow adjustment for the following variables:

- Baseline Ishak Fibrosis Score
- Immunosuppression regimen (classified into one of five groups: tacrolimus with/without steroids; cyclosporine with/without steroids; other)
- Age of the transplant donor
- Age of the recipient

Subgroup analyses of the model covariates, stated above, will also be conducted.

Shift tables of changes in Ishak Fibrosis Score over time will also be presented.

Secondary Endpoint

Estimates of the treatment effect of IDN-6556 versus placebo, and corresponding 95% confidence intervals of the modified Histological Activity Score will be conducted applying the suitable model for ordinal categorical data and detailed in the Statistical Analysis Plan. Shift tables showing changes over time will also be presented.

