9.1 PRIMARY EFFICACY ANALYSIS

All screening and post-baseline biopsy data collected will be used in the primary analysis, irrespective of the defined protocol visit window. Classification of the Ishak fibrosis score will be summarized descriptively by treatment group at baseline, Month 12, and Month 24. Response at Months 12 and 24 will be summarized descriptively by treatment group, along with exact (Clopper-Pearson) 95% confidence intervals (CIs). The risk difference between groups will also be provided with its 95% CI.

For the primary efficacy analysis based on the Month 24 biopsy, subjects with a missing Month 24 biopsy will have their Ishak fibrosis score imputed. Imputation of missing Ishak fibrosis scores will be conducted using multiple imputation (MI). Results will be imputed based on age, gender, baseline Ishak fibrosis score, and the Month 12 Ishak fibrosis score. Imputations will be based on at least 5 imputed datasets, depending on the percent of missing observations and will be documented in the clinical study report. Within each imputed dataset, the change from baseline at Month 24 will be derived to allow categorization into response or no response as defined in [Section 5.1](#).

Study success will be determined per the criteria described in [Section 0](#). This primary analysis will be conducted using the FAS.

The following sensitivity analyses will be provided for the primary efficacy endpoint, using different methods for the handling of missing liver biopsy results at Month 24:

- All FAS observed post-baseline biopsies
- All FAS observed post-baseline at Month 24 (within the sensitivity analysis visit window, per [Section 3.5](#))
- FAS with missing M24 biopsy imputed to ‘No’ response
- Per-protocol

Response rates at Month 12 will be summarized using the FAS in the same manner as the response rates at Month 24 (i.e., using MI). Subjects with a missing Month 12 liver biopsy will have their Month 12 Ishak fibrosis score imputed based on age, gender, and baseline Ishak fibrosis score.

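### The protocol defines no path for a subject who stops study drug but stays in the study, and the primary Month 24 biopsy after discontinuation depends on a separate consent, so primary data may be missed avoidably

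*Protocol*

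**What the plan says.** Protocol 8.6.1 covers early termination. Subjects who leave prematurely, "regardless of the cause, will be contacted and asked to sign a separate consent to return for a Month 24 liver biopsy". The same request appears in the synopsis, 6.0, 8.1.1, 8.3, 8.3.2 and Appendix I footnote F. The rest of the pathway is a set of End of Treatment assessments on the day of discontinuation and one visit four weeks later. If discontinuation falls within about 42 days of Month 24, the biopsy may be taken then.

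The possible reasons for removal from the study in 8.6.1 include "the subject does not adhere to study rules and procedures", an adverse event and an unacceptable concomitant medication. Appendix I has one column for Month 24, early termination and end of treatment together, and no off-drug schedule.

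Three other places bear on this:
- Protocol 7.1, criterion 6, requires at entry: "Willing to undergo protocol-determined liver biopsies during the study".
- Protocol 12.6.3 has the primary analysis test the "change in Ishak Fibrosis Scores at 24 months between the treatment groups in the FAS Population using ITT principles".
- SAP 9.1 uses all collected biopsies whatever the visit window, and "subjects with a missing Month 24 biopsy will have their Ishak fibrosis score imputed". The listed predictors are age, gender, baseline score and Month 12 score. One sensitivity analysis counts a missing Month 24 biopsy as non-response.

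**The concern.** An intention-to-treat comparison at 24 months needs the Month 24 biopsy from subjects who stopped drug as well as from those who stayed on it. Here, a subject who merely stops the capsules has no defined route to remain a participant, and the primary endpoint is then reached through a second consent. Each opt-in step can be refused or missed, and those who accept may differ from those who do not.

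The trial is small. One subject is 1/20 = 5 points of the placebo response rate and 1/40 = 2.5 points of the active rate. A few absent biopsies could therefore move the result across the decision boundaries at 5 and 15 points (Protocol 12.5, SAP 4).

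**Working it through.** **1. Inputs.** Arm sizes: "Approximately 60 subjects (40 subjects on IDN-6556: 20 on placebo) will be assigned in a 2:1 ratio" (Protocol synopsis). Significance level: "All endpoints will be tested at a two-sided statistical significance level of 0.05" (synopsis). Placebo response: 30%, the base case in SAP 4. Protocol 12.5 states 80% power for a 37-point increase and 20% for a 15-point increase. It plans that "A total of 60 subjects will be treated in a 2:1 ratio to IDN-6556 or placebo" and makes no allowance for missing biopsies. Neither document gives a discontinuation or refusal rate, so 10%, 20% and 30% missing in each arm are assumptions.

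**2. The plan's own figures.** Power = Φ[(Δ − 1.96 × pooled SE) / unpooled SE].
- 30% vs 67%: pooled rate (26.8 + 6)/60 = 0.547; pooled SE = √(0.547 × 0.453 × 0.075) = 0.136; unpooled SE = √(0.67 × 0.33/40 + 0.21/20) = 0.127. Power is 79.2%, against 80% stated.
- 30% vs 45%: power is 19.1%, against 20% stated.

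The stated power is therefore that of a trial with all 40 and 20 subjects evaluable.

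**3. Effect of missing biopsies.** If a fraction m of an arm is unobserved, its response rate can lie anywhere in an interval of width m. The bounds on the difference then have width m(active) + m(placebo), whatever the response rate. At 30% response, SE = √(0.21/n₁ + 0.21/n₀). The power column is for observed cases only.

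| Missing per arm (assumed) | Evaluable | Width of bounds | SE at 30% response | Power at +37 points |
|---|---|---|---|---|
| 0% | 40/20 | 0 | √(0.21/40 + 0.21/20) = 12.5 points | 79.2% |
| 10% | 36/18 | 20 points | √(0.21/36 + 0.21/18) = 13.2 points | 74.6% |
| 20% | 32/16 | 40 points | √(0.21/32 + 0.21/16) = 14.0 points | 69.3% |
| 30% | 28/14 | 60 points | √(0.21/28 + 0.21/14) = 15.0 points | 63.1% |

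The middle decision category is 15 − 5 = 10 points wide. The SE ratio at 20% missing, √(1/0.8) = 1.12, does not depend on the response rate. The primary analysis imputes, so Month 12 scores may win back some precision; the SE and power columns do not include that.

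**4. Selective loss.** Let p be the true response rate in an arm, d the fraction without a biopsy and r the response rate in that fraction. The observed rate is (p − d·r)/(1 − d). Take no drug effect and p = 30% in both arms.
- r = 0, loss 25% active vs 10% placebo: 0.30/0.75 − 0.30/0.90 = 40.0% − 33.3% = +6.7 points. At 20% vs 10% it is +4.2, and at 30% vs 10% it is +9.5.
- r = 15%: +2.1, +3.3 and +4.8 points for 20%, 25% and 30% active loss against 10% placebo loss.
- Equal loss in both arms with the same r: 0 points.

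Bias here needs loss that differs between arms. In the r = 0 cases, 25% or 30% active loss takes an observed-case difference past 5 points with no true effect.

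**5. What the imputation can repair.** The four listed predictors in SAP 9.1 include neither treatment arm nor whether the subject stopped. A stopper is therefore imputed as if like a subject who stayed with the same age, gender and scores. Someone who stops before Month 12 will normally have no Month 12 score either, because the request after discontinuation names Month 24 only.

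**The case against.** The strongest reply is that retrieval is already the plan. Every subject who discontinues is asked, whatever the cause, so non-adherent subjects are not filtered out. The biopsy can be taken at discontinuation near Month 24. Protocol 8.1.1 calls for reasonable attempts at continued follow-up. SAP 9.1 uses every retrieved biopsy, imputes the rest and adds a missing-as-non-response analysis, which would give the right answer in the r = 0 cases above. This stands. A reader might infer that primary data are lost by design, or that an adherence filter is built into data collection; the documents support neither.

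A reader might also infer that leaving the study is the only exit. That goes too far. Protocol 13.1 foresees permanent discontinuation of study drug. Section 10.0 leaves continued participation open after one kind of drug stop. Section 8.4 keeps subjects in all procedures after immunosuppressant changes. SAP 8.1 tabulates drug discontinuation and study withdrawal separately. The removal reasons in 8.6.1 are permissive. But these passages recognise an off-drug participant without saying what is then collected. The follow-up in 8.1.1 runs for a period that 8.3.3 describes as a single visit four weeks after treatment.

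Nor do the documents say when the separate consent is sought. It could be signed at the early termination visit, so a delay of nearly two years is a possibility and not a stated rule.

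Finally, the calculations cover missing biopsies from any cause, including death and refusal, which consent wording would not fully recover. That also stands.

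**Conclusion.** The point holds as a cheap improvement. The protocol leaves the off-drug participant undefined and adds an opt-in step before the primary biopsy of subjects who discontinue. This risks avoidable and possibly selective missing data, and the imputation does not account for stopping.

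The size rests on assumed loss. At 10% to 30% missing per arm, the no-assumption bounds are 20 to 60 points wide, against a 10-point middle category. At 20% missing and 30% response, the SE rises from 12.5 to 14.0 points. Bias arises in the scenarios above only if loss differs between arms; equal, equally selective loss costs precision alone. The share of missing biopsies that the change would recover is unknown.

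**What to change.** In Protocol 8.6.1, 8.1.1, 8.3.2 and Appendix I footnote F, define 'stopped study drug' separately from 'withdrew consent to the study'. Leave the rules on who stops drug as they are.

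State in the main consent form that a subject who stops study drug for any reason, including non-adherence or a disallowed medication, remains in the study for the Month 24 biopsy and the scheduled outcome contacts, and may still decline either. Keep the separate consent only for subjects who withdrew consent to the study.

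A Month 12 biopsy for subjects who stop before then is not part of this change. The plan does not now request it, and it would be an added invasive procedure.

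The cost is protocol and consent wording, plus some extra site contact with off-drug subjects. The Month 24 biopsy itself is already requested from everyone who discontinues.
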